At least 1 clinical response (minimum of stable disease ~16 weeks) must be seen in any of the first 10 patients treated at the RP2D in order to fully enroll either expansion cohort. These 10 patients include the patients enrolled under the 3+3 design for DLT assessment; if necessary, additional patients will be enrolled to a maximum of 10 patients. If no clinical responses are observed, the study will be stopped for futility. If a clinical response is observed at any time, then enrollment of the full expansion cohort may proceed. Initiation of the KPT-9274 + niacin ER escalation will not be dependent upon demonstration of clinical benefit of the single agent, but futility at the KPT-9274 + niacin ER RP2D will be assessed prior to full expansion using the same criterion as described above for the single agent KPT-9274.

The KPT-9274 ± niacin ER expansion cohort will consist of 4 groups of approximately 45 patients (please note that these expansion groups may change based on escalation results) including:

- I. NAPRT1 deficient tumor group, approximately 10 patients
- II. NAPRT1 positive tumor group, approximately 10 patients
- III. Either NAPRT1 deficient or positive tumor group, approximately 10 patients
- IV. IDH1 mutant tumor group, approximately 15 patients

Please note that the composition of the expansion groups (e.g., number of patients with NAPRT1 positive vs NAPRT1 deficient tumors) may change based on the results from the escalation phase. An additional, optional KPT-9274 single agent expansion cohort will consist of ~ 20 patients with any tumor mutational status.

Patients in the Dose Expansion Phase may be treated with the RP2D of KPT-9274 ± niacin ER according to the same schedule administered in the Dose Escalation Phase of the study.

Patients who are in Part A or Part B of the Dose Escalation Phase being treated at the RP2D ± niacin ER dose chosen for expansion will be included in the efficacy and safety analyses of the Dose Expansion Phase.

Part C: KPT-9274 + Nivolumab

After sufficient data from Part A is available, Dose Finding with the potential for Expansion in patients with melanoma will be conducted to further explore safety, tolerability and preliminary evidence of anti-tumor activity of the RP2D (or any DLT-cleared dose) of KPT-9274 + nivolumab.

DOSE FINDING PHASE

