2.2.2. Efficacy Endpoints

Disease response will be evaluated according to RECIST 1.1 (advanced solid malignancies and melanoma ([Appendix 4](#))) or Lugano Classification (NHL) ([Appendix 3](#)) and will include the following:

- **Overall response rate (ORR):** = proportion of patients who have a response of partial response (PR) or complete response (CR).
- **Duration of response (DOR):** the duration of time from first meeting CR or PR measurement criteria (whichever occurs first) until the first date that PD recurrence is objectively.
- **Disease control rate (DCR):** DCR = proportion of patients who have a response of CR, PR, and Stable Disease (SD) ≥ 16 weeks.
- **Duration of disease control:** the duration of time from date of first study treatment until the first date that PD is objectively documented.
- **Progression-free survival (PFS):** the duration of time from date of first study treatment until the first date that PD is objectively documented or death due to any cause.
- **Overall survival (OS):** the duration of time from date of first study treatment until death from any cause .

- **Time to Progression (TTP):** The duration of time from date of first study treatment until the first date that PD is objectively documented or death due to PD.

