6.2.3. Dosing Information

Patients will receive oral KPT-9274 three times a week every other day (Days 1, 3, 5, 8, 10, 12, 15, 17, 19, 22, 24, and 26) during each 28-day cycle.

Study treatment will be administered in the clinic and at home as indicated in [Table 4](#). Study treatment dosing will occur in the clinic during Cycle 1 on Days 1, 3, 8, 15, 22, 24, and 26, during Cycle 2 on Days 1, 8, 15, and 22, and during \geq Cycle 3 on Days 1 and 15. Study treatment dosing will occur at home during Cycle 1 on Days 5, 10, 12, 17, and 19, during Cycle 2 on Days 3, 5, 10, 12, 17, 19, 24, and 26 and during Cycles \geq 3 on Days 3, 5, 8, 10, 12, 17, 19, 22, 24, and 26.

During Part B of the Dose Escalation Phase, patients will receive 500 mg niacin ER co-administered with each dose of KPT-9274. The starting dose of 500 mg niacin ER may be titrated to 2,000 mg of daily dose, per label. The starting dose for KPT-9274 in Part B will be a dose and schedule that cleared DLT assessment during Part A. For the purposes of dose escalation decisions, a standard 3+3 dose escalation design will be used during both Part A and Part B.

A total of ~65 patients with advanced solid malignancies and NHL may be enrolled to further explore safety, tolerability and preliminary evidence of anti-tumor activity of the RP2D of KPT-9274 \pm niacin ER. After declaring the RP2D \pm niacin ER (see Section [6.2.6](#)), based on the safety and tolerability results of the Dose Escalation Phase, a decision will be made whether expansion (4 groups, ~45 patients total) will be conducted at the RP2D of KPT-9274 single agent or at the RP2D of KPT-9274 + niacin ER. If the 45 patient expansion is conducted at the RP2D of KPT-9274 + niacin ER, an optional expansion with < 20 patients at the RP2D of KPT-9274 single agent may be initiated. Futility analyses based on clinical efficacy will be conducted in a maximum of 10 patients dosed at the RP2D \pm niacin ER (see Section [6.2.7](#) for additional details).

Dose escalation will occur according to the Dose Escalation Guidelines provided in Section [6.2.6](#).

Patients with melanoma enrolled in Part C, KPT-9274 + nivolumab, cohort will receive nivolumab (480 mg once per 28 day cycle) according to the current prescribing information.

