At least 1 clinical response (minimum of stable disease ~8 weeks) must be seen in any of the first ten patients treated at the RP2D in order to fully enroll either expansion cohort. These 10 patients include the patients enrolled under the 3+3 design for DLT assessment; if necessary, additional patients will be enrolled to a maximum of 10 patients. If no clinical responses are observed, the study will be stopped for futility. If a clinical response is observed at any time, then enrollment of the full expansion cohort may proceed. Initiation of the KPT-9274 + niacin ER escalation will not be dependent upon demonstration of clinical benefit of the single agent, but futility at the KPT-9274 + niacin ER RP2D will be assessed prior to full expansion using the same criterion as described above for the single agent KPT-9274.

The KPT-9274 ± niacin ER expansion cohort will consist of 4 groups of approximately 45 patients (please note that these expansion groups may change based on escalation results) including:

- NAPRT1 deficient tumor group, approximately 10 patients
- NAPRT1 positive tumor group, approximately 10 patients
- Either NAPRT1 deficient or positive tumor group, approximately 10 patients
- IDH1 mutant tumor group, approximately 15 patients

Please note that the composition of the expansion groups (e.g. number of patients with NAPRT1 positive vs NAPRT1 deficient tumors) may change based on the results from the escalation phase.

An additional, optional KPT-9274 single agent expansion cohort will consist of < 20 patients with any tumor mutational status.

Patients in the Dose Expansion Phase may be treated with the RP2D of KPT-9274 ± niacin ER according to the same schedule administered in the Dose Escalation Phase of the study.

Patients who are in Part A or Part B of the Dose Escalation Phase being treated at the RP2D ± niacin ER dose chosen for expansion will be included in the efficacy and safety analyses of the Dose Expansion Phase.

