7.3.3.1. CT, MRI, PET-CT, or Imaging Methodology Per Investigator Discretion

Disease response is based on tumor measurement using computed tomography (CT) scans or, magnetic resonance imaging (MRI) scans, or PET-CT, or imaging methodology per Investigator discretion. Scans will be performed at Screening (Day -30 to Day -1), then every 8 weeks \pm 7 days (e.g., Day 1 of odd numbered cycles) until disease progression or the EoT visit. EoT scan is only required for patients who end treatment for reasons other than disease progression.

The same scan modality should be used for all assessments.

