9.5.1. Futility Testing

For Part A or Part B, at least one clinical response (minimum of stable disease ~16 weeks) must be seen in any of the first ten patients treated at the RP2D in order to fully enroll either expansion cohort. These 10 patients include the patients enrolled under the 3+3 design for DLT assessment; if necessary, additional patients will be enrolled to a maximum of 10 patients. If no clinical responses are observed, the study will be stopped for futility. If a clinical response is observed at any time, then enrollment of the full expansion cohort may proceed. Initiation of the KPT-9274 + niacin escalation will not be dependent upon demonstration of clinical benefit of the single agent, but futility at the KPT-9274 + niacin RP2D will be assessed prior to full expansion using the same criterion as described above for the single agent KPT-9274.

[figure not shown]

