#### DOSE EXPANSION PHASE

After completion of the Dose Escalation Parts A and B, Dose Expansion in up to 65 additional patients with advanced solid malignancies and NHL may be conducted to further explore safety, tolerability and preliminary evidence of anti-tumor activity of the RP2D of KPT-9274 ± niacin ER. Note that preliminary clinical results may define the patient population (i.e., specific indications) selected for enrollment in the Dose Expansion Phase.

After declaring the RP2D for KPT-9274 single agent and KPT-9274 + niacin ER, based on the safety and tolerability results of the Dose Escalation Phase, a decision will be made whether expansion (4 groups, ~45 patients total) will be conducted at the RP2D of KPT-9274 single agent or at the RP2D of KPT-9274 + niacin ER. If the ~45 patient expansion is conducted at the RP2D of KPT-9274 + niacin ER, an optional expansion with < 20 patients at the RP2D of KPT-9274 single agent may also be initiated.

At least 1 clinical response (minimum of stable disease ~16 weeks) must be seen in any of the first 10 patients treated at the RP2D in order to fully enroll either expansion cohort. These 10 patients include the patients enrolled under the 3+3 design for DLT assessment; if necessary, additional patients will be enrolled to a maximum of 10 patients. If no clinical responses are observed, the study will be stopped for futility. If a clinical response is observed at any time, then enrollment of the full expansion cohort may proceed. Initiation of the KPT-9274 + niacin ER escalation will not be dependent upon demonstration of clinical benefit of the single agent, but futility at the KPT-9274 + niacin ER RP2D will be assessed prior to full expansion using the same criterion as described above for the single agent KPT9274.

The KPT-9274  $\pm$  niacin ER expansion cohort will consist of 4 groups of approximately 45 patients (please note that these expansion groups may change based on escalation results) including:

- I. NAPRT1 deficient tumor group, approximately 10 patients
- II. NAPRT1 positive tumor group, approximately 10 patients
- III. Either NAPRT1 deficient or positive tumor group, approximately 10 patients
- IV. IDH1 mutant tumor group, approximately 15 patients

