# 1.6. INTERIM ANALYSIS

No interim analysis is planned for this study.

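### The futility gate for dose expansion has two minimum stable-disease durations, about 8 weeks in Protocol 6.2.7 and about 16 weeks everywhere else

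*Protocol*

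**What the plan says.** The gate appears four times in current text, and apart from the duration the rule is the same each time.

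- Protocol 6.2.7 (dose schedule for the expansion phase): "At least 1 clinical response (minimum of stable disease ~8 weeks) must be seen in any of the first ten patients".
- Protocol 9.5.1 (Futility Testing): "at least one clinical response (minimum of stable disease ~16 weeks) must be seen in any of the first ten patients".
- Protocol synopsis, Dose Expansion Phase: "At least 1 clinical response (minimum of stable disease ~16 weeks) must be seen in any of the first 10 patients".
- SAP 1.1, Dose Expansion Phase: "At least 1 clinical response (minimum of stable disease ~16 weeks) must be seen in any of the first 10".

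All four count the 3+3 patients towards the ten, stop the study for futility if no response is seen, allow full enrolment as soon as one is seen, and apply the criterion separately to the niacin combination.

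Protocol 6.2.3 gives no duration. It says "Futility analyses based on clinical efficacy will be conducted in a maximum of 10 patients dosed at the RP2D" and refers to 6.2.7 for the details.

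Two other places bear on the point. Protocol 7.3.3.1 sets the imaging schedule: "Scans will be performed at Screening (Day -30 to Day -1), then every 8 weeks", with a 7-day window. Protocol 2.2.2 defines disease control: "DCR = proportion of patients who have a response of CR, PR, and Stable Disease (SD) ≥ 16 weeks".

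**The concern.** This is the study's stop/go rule for expansion, and it has two thresholds. A team working from the treatment section would apply about 8 weeks. A statistician working from the statistical section or the SAP would apply about 16. Neither document has a precedence clause. SAP 1.7 reports no modification to the protocol's statistical section, which is consistent with 9.5.1 but leaves 6.2.7 unreconciled.

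The gate controls an expansion of about 45 patients and an optional single-agent cohort of up to 20. Because enrolment may proceed once a response is seen, a team following 6.2.7 could start enrolling about 8 weeks before stable disease could be judged against the other version. The trial is open-label, so an unresolved threshold could also end up being chosen after the outcomes are known.

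**Working it through.** **1. Are these one rule or two?** The number of patients, the minimum count, the consequence of failing and the separate application to the niacin combination agree in all four statements. Only the duration differs. It is one rule with two thresholds.

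**2. Can the approximation sign bridge the gap?** No. With scans every 8 weeks ± 7 days, the first post-baseline scan falls in weeks 7 to 9 and the second in weeks 15 to 17. The two durations correspond to different scans.

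**3. Which way can they disagree?** A patient stable for about 16 weeks was also stable at about 8, so the 16-week criterion is nested in the 8-week one. I take a CR or PR at any scan as meeting both versions. The only possible conflict is therefore that 6.2.7 opens while 9.5.1 stops. One case is enough: no CR or PR among the ten, one patient stable at week 8 who progresses by week 16, and the other nine progressed by week 8.

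**4. How often could that happen?** The plan gives no target rate, error rate or power for the gate, so there is no stated figure to reproduce. What follows is an illustration on assumed rates.

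- Chance that the gate opens with per-patient qualifying probability p: 1 − (1 − p)^10.
- p8 = chance that a patient has not progressed at 8 weeks (assumed, shown as a range).
- Constant hazard (assumed): p16 = p8².
- Because the criteria are nested, P(opposite decisions) = P(open, 8 weeks) − P(open, 16 weeks).

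Example at p8 = 0.20: 1 − 0.80^10 = 0.893. With p16 = 0.04, 1 − 0.96^10 = 0.335. The difference is 56 percentage points.

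| p8 | p16 | Opens, 8-week version | Opens, 16-week version | Opposite decisions (points) |
|---|---|---|---|---|
| 5% | 0.25% | 40% | 2% | 38 |
| 10% | 1% | 65% | 10% | 56 |
| 20% | 4% | 89% | 34% | 56 |
| 30% | 9% | 97% | 61% | 36 |
| 40% | 16% | 99% | 83% | 17 |
| 50% | 25% | 99.9% | 94% | 6 |
| 60% | 36% | 99.99% | 98.8% | 1 |
| 70% | 49% | >99.99% | 99.9% | 0.1 |

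Simulating 400,000 sets of ten patients at p8 = 10%, 20%, 30% and 50% gave 0.557, 0.558, 0.363 and 0.055 for opposite decisions, and none in the reverse direction.

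**5. Effect of early responders.** Suppose a fraction r = 5% of patients have a CR or PR at the first scan and count under both versions whatever follows. Then the 16-week qualifying probability is r + (p8 − r) × p8.

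| p8 | 16-week qualifying probability | Opens, 8-week version | Opens, 16-week version | Opposite decisions (points) |
|---|---|---|---|---|
| 5% | 0.050 | 40% | 40% | 0 |
| 10% | 0.055 | 65% | 43% | 22 |
| 20% | 0.080 | 89% | 57% | 33 |
| 30% | 0.125 | 97% | 74% | 23 |
| 40% | 0.190 | 99% | 88% | 12 |
| 50% | 0.275 | 99.9% | 96% | 4 |

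**The case against.** The strongest reply is that a workable rule exists. The section headed Futility Testing, the synopsis and the SAP agree, and the outlier is one sentence in a treatment section. Expansion is optional, and passing the gate permits full enrolment without compelling it. This limits when the conflict bites but does not remove it. Failing the gate is stated as a mandatory stop, and 6.2.3 directs readers to the outlier.

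The probabilities are also open to challenge. No rate or hazard shape comes from the documents. If patients stable at 8 weeks progress more slowly afterwards, the gap shrinks, and above a p8 of about 60% it almost vanishes. That stands, and the peak of 56 points should not be read as an estimate.

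The documents also do not say outright that a response at the first scan followed by progression before 16 weeks satisfies the 16-week version. Counting it is a reading of the provision that a response at any time allows enrolment, and the early-responder figures depend on it.

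Finally, three statements against one is weak evidence of intent, because the synopsis and SAP texts are near-verbatim copies.

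**Conclusion.** The contradiction is real and lies entirely within current text; it does not rest on the amendment log. The same ten patients can open full expansion under Protocol 6.2.7 and stop the study under 9.5.1, and no passage settles which applies.

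The finding does not depend on the probabilities. On the assumed constant hazard without early responders, the chance of opposite decisions runs from 56 points at p8 of 10% or 20% down to about 0.1 at 70%. With 5% early responders counted, the largest gap in the range shown is 33 points. Where between these the trial would fall is unknown. Because a mandatory stop rule gives two answers from the same data, it must be fixed before the gate is applied.

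**What to change.** Have the sponsor confirm one duration before the gate is assessed, and reconcile Protocol 6.2.7, the synopsis, Protocol 9.5.1 and SAP 1.1 to it. State the criterion once, most naturally in 9.5.1 because that is the futility section, and let 6.2.3 and 6.2.7 refer there instead of restating it. The same sentence could say whether a CR or PR counts whatever its duration.

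The documents do not prove which duration was intended. About 16 weeks matches the disease control definition and needs one protocol line changed, but the futility decision then waits for about the second scan when there is no earlier response. About 8 weeks allows an earlier decision but means changing three statements, and the gate would no longer match the DCR definition. Either way the cost is a few lines of text and a cross-reference, with no new data.

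A separate, minor point: SAP 1.6 says "No interim analysis is planned for this study"; a clause excepting the futility gate would avoid confusion.

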6.2.8. KPT-9274 Dose Reduction Guidelines for Toxicity

For Grade 2 toxicities present at baseline, the drug will not be held and the treating investigator will closely monitor and support the patient.

Patients are expected to be aggressively treated to minimize the likelihood and/or severity of side effects at the discretion of the Investigator (consultation with the Karyopharm Medical Monitor is strongly encouraged), particularly GI symptoms and hematopoietic toxicities as observed in KPT-9274 animal toxicology studies. See Section [6.9.1](#) for supportive care details.

For patients who do not tolerate the protocol-specified dosing schedule, KPT-9247 dose adjustments are permitted in order to allow the patient to continue the study treatment. The criteria for dose modifications of KPT-9274 for toxicities are outlined in [Table 15](#). These changes must be recorded on the eCRF. If a patient requires a dose delay of more than 28 days (> 28 days) from the intended day of the next scheduled dose, then the patient should be discontinued from the study (in exceptional situations, if the patient is clearly benefiting from the study treatment, and in the opinion of the Investigator no safety concerns are present, after discussion with the Karyopharm Medical Monitor, the patient may remain in the study).

If, after interruption of treatment and resolution of the event, treatment is resumed at the same dose and the same toxicity reoccurs with the same severity, the next treatment re-initiation must resume at the next lower dose level, irrespective of duration. Patients who do not recover (i.e., ≤ Grade 1 or baseline) within 28 days (≤ 28 days) of discontinuation of study treatment will not be permitted to re-start study treatment and will be discontinued from the study.

In the event of a DLT (Cycle 1) during the Dose Escalation Phase the patient must discontinue KPT-9274.

In the event of any other toxicity (< Grade 3) during the Dose Escalation Phase, one of the following actions may be taken at the Investigator's discretion after consulting with the Karyopharm Medical Monitor:

- Patients can continue treatment with KPT-9274 without a dose delay or reduction.
- If the decision is made to hold KPT-9274:
 - Patients may be re-started on KPT-9274 either at the original dose OR at one dose level lower upon recovery to Grade ≤ 1 or baseline (see [Table 15](#) for pre-specified dose modifications for AEs and [Table 16](#) for dose modification guidelines for KPT-9274).

For the Dose Expansion Phase, if an event meeting the definition of a DLT, but without necessarily occurring within the first 28 days, is observed in > 33% of patients at any time, or if > 33% of treated patients have withdrawn consent due to toxicity, enrollment will be held and a meeting with all investigators and Karyopharm/Medical Monitor will take place to review the

events and discuss their clinical significance. Based on this review, the sponsor may elect to reduce the dose for enrolled patients and to resume enrollment of the expansion cohort at this lower dose, or the enrollment into the expansion cohort will be stopped.

[Table 15](#) summarizes the pre-specified dose modifications (i.e., Dose Levels 1 through 5+) for AEs listed in [Table 16](#).

Table 15: Pre-specified Dose Modifications for Adverse Events

Dose Level	KPT-9274 Dose (mg) (Dose Escalation, Part A and Part B)*
5+	Increase in 20 mg increments
4	40 mg
3	30 mg
2	20 mg
1	10 mg

*From the RP2D, patients will be dose reduced by 1 dose level increments as needed as in [Table 16](#).

For dose reduction, find the current dose in [Table 15](#) and reduce as indicated in [Table 16](#).

Table 16: KPT-9274 Dose Modification and Supportive Care Guidelines

Toxicity and Intensity	Dose Modification
Non-hematologic Toxicity	
Grade 1	
Maintain dose.
 
Consider instituting supportive care medications per institutional guidelines. For additional options, see NCCN Clinical Practice Guidelines in Oncology for Fatigue, Palliative Care, and Antiemesis, also refer to Benson guidelines.

Grade 2	
Institute supportive care medications per institutional guidelines. For additional options, see NCCN Clinical Practice Guidelines in Oncology for Fatigue, Palliative Care, and Antiemesis, (also refer to Benson Guidelines).
 
For Grade 2 toxicities, the Investigator should consult with the Karyopharm Medical Monitor when deciding on treatment delays or modifications. If modifications are desired, guidelines for AEs \geq Grade 3 should be followed. At the Investigator's discretion after consulting with the Karyopharm Medical Monitor, patients may continue on KPT-9274 uninterrupted at their current dose.

\geq Grade 3	
Optimal supportive care medications according to institutional guidelines or NCCN Clinical Practice Guidelines in Oncology should already be instituted. Also refer to Benson Guidelines.
 
Hold KPT-9274 until the event resolves to \leq Grade 1 or baseline (as appropriate):
 
 First occurrence of \geq Grade 3: 
 If supportive care results in the AE improving to Grade \leq 1 or baseline within 3 days (\leq 3 days), restart KPT-9274 at the current dose. If the improvement to Grade \leq 1 or baseline takes longer than 3 days ($>$ 3 days), KPT-9274 should be resumed at one dose level lower (see Table 15). Second or greater occurrence of \geq Grade 3, restart KPT-9274 at one dose level lower (see Table 15) upon improvement to Grade \leq 1 or baseline irrespective of duration. 
**If the toxicity does not resolve to \leq Grade 1 or baseline within 28 day (\leq 28 days), study treatment will be discontinued permanently.
 
**If, after interruption of treatment and resolution, treatment is resumed at the same dose and the same toxicity reoccurs with the same severity, next treatment re-initiation must resume at the next lower dose level, irrespective of duration.

Toxicity and Intensity	Dose Modification
Hematological Toxicity	
Thrombocytopenia	
Grade 2	Maintain dose
\geq Grade 3 without bleeding	
Follow institutional guidelines for Grade 3 or 4 thrombocytopenia without bleeding. Transfusions are allowed per institutional guidelines.
 
Hold KPT-9274 until resolves to \leq Grade 1 or baseline (maximum of 28 days, \leq 28 days):
 
 First occurrence of \geq Grade 3: 
 If improves within 7 days (\leq 7 days), restart KPT-9274 at the current dose. If the improvement takes longer than 7 days ($>$ 7 days), KPT-9274 should be resumed at one dose level lower. (see Table 15). Second or greater occurrence of \geq Grade 3, restart KPT-9274 at one dose level lower (see Table 15) upon improvement to Grade \leq 1 or baseline irrespective of duration. 
**If the toxicity does not resolve to \leq Grade 1 or baseline within 28 days (\leq 28 days), study treatment will be discontinued permanently.
 
**If, after interruption of treatment and resolution, treatment is resumed at the same dose and the same toxicity reoccurs with the same severity, next treatment re-initiation must resume at the next lower dose level (see Table 15), irrespective of duration.

\geq Grade 3 with bleeding	
Follow institutional guidelines for Grade 3 or 4 thrombocytopenia with bleeding. Transfusions are allowed per institutional guidelines.
 
Hold KPT-9274 until resolves to Grade \leq 1 or baseline and restart at one dose level lower (see Table 15).

Neutropenia	
\geq Grade 3 neutropenia without fever	
Implement growth factors per institutional guidelines.
 
Hold KPT-9274 until resolves to Grade \leq 1 or baseline and restart at one dose level lower (see Table 15).

\geq Grade 3 neutropenia with fever (febrile neutropenia)	
Implement growth factors and broad anti-microbial coverage per institutional guidelines.
 
Hold KPT-9274 until the event resolves to Grade \leq 1 or baseline and restart at one dose level lower (see Table 15).

All other hematologic Toxicity	
Grade 1 or 2	Maintain dose
\geq Grade 3	
Implement growth factors and broad anti-microbial coverage per institutional guidelines.
 
Transfusions (e.g., RBCs for anemia) are allowed per institutional guidelines.
 
Consider holding KPT-9274 until the event resolves to Grade \leq 1 or baseline and restart at one dose level lower (see Table 15). At the discretion of the Investigator after consulting with the Karyopharm Medical Monitor, patient may be treated with KPT-9274 without dose delays or modifications while receiving transfusions and/or growth factor support per institutional guidelines.

All dose modifications should be based on the worst preceding toxicity.	
*Isolated values of \geq Grade 3 alkaline phosphatase values will NOT require dose interruption. Determination of liver vs. bone etiology should be made, and evaluation of gamma-glutamyl transferase (GGT), 5'-nucleotidase (5'NT), or other liver enzymes should be performed.	
Note: for combinations of Grade 1 or 2 adverse events (e.g., nausea, fatigue, anorexia) that significantly impair the patient's quality of life, 1-2 doses of study treatment may be skipped after consultation with the Karyopharm Medical Monitor and supportive care per institutional guidelines has been implemented. Study treatment may then be restarted after consultation with the Karyopharm Medical Monitor.	
Benson AB, Ajani JA, Catalano RB, et al.	

